6.2.5 Completion/Final Evaluation

Month 12 Follow-up

In addition to outcomes collected weekly and monthly, the following outcomes will be collected at month 12 (between -14 and +28 days)

- Secondary outcomes
 - Satisfaction, global improvement, chronic interference with daily activities, visual trajectory questionnaire for pain¹⁸⁶ and SBST status
 - Chronic LBP status as determined by NIH RTF questions
- Psychosocial mediator measures
 - Self-efficacy, Coping, Kinesiophobia, and Pain Catastrophizing measures
 - Measurement of key non-specific factors that may influence outcomes will be measured using the short form positive outlook (6-item) from the Healing Encounters and Attitudes Lists (HEAL)
- Intervention uptake (SSM, SSM+SMT participants only)
- COVID-19 impact
- Participant Close-out
 - Final participation will be used to record participant status

All efforts will be taken to facilitate participant's completion of the study interventions. In the event a participant must discontinue the intervention early (see also Intervention Discontinuation), participants will be asked to complete follow-up electronic self-report questionnaires to the extent possible. Potential reasons for early termination include:

- Participant develops a competing comorbid health condition that precludes adherence or makes it unsafe for them to proceed with their assigned treatment.
- A change in the participant's life (e.g., participant moves, dies, has other personal matters to attend).
- Participant chooses to discontinue on their own for any reason (e.g., participant is not responding to care or getting worse).
- Study closure by institute or oversight body.

Additional information related to intervention discontinuation is described in Section 8.

6.2.6 Additional Evaluation Related to Hybrid Effectiveness/Implementation Design, RE-AIM and PRECIS Frameworks

Implementation Measures

Mixed-methods data collection (qualitative and quantitative) will be used to collect contextual information addressing dimensions outlined by the RE-AIM framework. These data will inform future implementation and aid in the interpretation of effectiveness results.²⁵

Screening

- Qualitative survey questions (open-ended) will assess potential participants' views regarding barriers and facilitators to participating in the study and study interventions.
- Quantitative data regarding reasons for exclusion will also be collected

Months 2, 6, and 12 Follow-Up

- Qualitative surveys will address enrolled participants barriers and facilitators to engaging in the interventions as recommended, including barriers and facilitators for engaging in telehealth visits.
- Satisfaction
- HEAL Positive Outlook

Additional contextual data will be collected from the participating practitioners to inform future implementation in other settings. Prior to training, prior to the start of the UG3 pilot phase, at the completion of the UG3 pilot phase, pre and post UH3 training, annually during the UH3, and at the completion of the UH3 randomized controlled trial, self-report questionnaires will be administered to all participating practitioners. Questionnaires will include qualitative survey questions that address practitioners' views regarding the interventions, including perceived barriers and facilitators and their confidence in the interventions and in delivering care remotely¹⁸⁹. The Pain Attitudes and Beliefs Scale (PABS)⁴³ and additional questions regarding practitioner confidence (using a 0-10 NRS) will also be assessed quantitatively in the self-report questionnaires.

Qualitative data will also be collected from purposeful samples of health providers' and health system leaders using data collection methods that meet their needs and preferences (e.g., qualitative surveys, interviews and field notes). Additional details regarding assessment of implementation measure data collection is provided in the manual of operations.

7. SAFETY ASSESSMENTS

7.1 Specification of Safety Parameters

Following enrollment, participants will be asked about the occurrence of AE/SAEs by their treatment provider at every visit. In addition, participants will be informed to report AE/SAEs directly to study staff throughout the study period and will also be asked if they experienced any AE/SAEs associated with study interventions on monthly self-report surveys. Events will be followed for outcome information until resolution or stabilization. The PI or designee will record all reportable events with start dates occurring any time after enrollment until 7 (for non-serious AEs) or 30 days (for SAEs) after the last day of study participation.

7.2 Methods and Timing for Assessing, Recording, and Analyzing Safety Parameters

Spinal manipulation therapy (SMT) is considered safe for the treatment of LBP, but side effects associated with SMT are common and benign. Approximately 50% of patients report one reaction, most commonly local discomfort that resolves within a day.⁷⁹⁹⁻¹⁰² SAEs following lumbar SMT are rare⁷ and are estimated to occur once per million to several million visits and include cauda equina syndrome, disc herniation, fracture, hematomas or hemorrhagic cysts.¹²³

Risks associated with the supported self-management group are considered extremely rare. No SAEs were reported in trials including physical and biopsychosocial treatment components.⁷ Participants may experience emotional discomfort as a result of discussing the impacts of their pain (e.g., mood, social connections). Participants may also experience physical discomfort as a result of the directional preference, postural awareness, and strengthening exercises. All of these side effects are expected to be temporary and short-lasting.

Pharmacological therapies delivered as part of medical care are associated with increased AEs compared to placebo.⁷ Several protections are in place to minimize risks, including reminding participants to take their medication as prescribed and to contact the study clinician if there are changes to their medication regimens to avoid drug-drug adverse interactions. Also, clinicians will assess the potential for risk factors based on the patient's medical history prior to prescribing/recommending (prescription and OTC) medications and will suggest the lowest effective dose(s) for the shortest time necessary.

Below is an alphabetical list of expected AEs for each study intervention.

Supported Self-Management

- Emotional discomfort
- Exacerbation of low back pain
- New or increased leg pain
- Numbness or tingling
- Soreness or stiffness

Medical Care

- Allergic reaction
- Cardiovascular symptoms: hypotension, edema, flushing,
- Central nervous system: dizziness, weakness, ataxia, fatigue, drowsiness, headache, stimulation, insomnia, sedation, tremor, syncope
- Chemical dependence
- Dermatologic: itchy skin, rash, sweating
- Endocrine & Metabolic: weight gain
- Exacerbation of low back pain
- Gastrointestinal symptoms: nausea, vomiting, dry mouth, abdominal pain, dyspepsia, diarrhea, GERD, constipation, bleeding
- Kidney failure (excessive NSAIDs use)
- Liver failure (excessive Acetaminophen use)
- Ophthalmic: visual field loss, blurred vision
- Respiratory: depression, arrest, apnea

Spinal Manipulation Therapy

- Cauda equina syndrome
- Disc herniation
- Exacerbation of low back pain
- Fracture
- Hematoma
- Hemorrhagic cyst
- New or increased leg pain
- Numbness or tingling
- Soreness or stiffness

7.3 Adverse Events (AEs) and Serious Adverse Events (SAEs)

AE is generally defined as any unfavorable and unintended diagnosis, symptom, sign (including an abnormal laboratory finding), syndrome or disease which either occurs during the study, having been absent at baseline, or if present at baseline, appears to worsen. AEs are to be recorded regardless of their relationship to the study intervention.

The following scale will be used to grade AEs:

1. Mild: no intervention required; no impact on activities of daily living (ADL).
2. Moderate: minimal, local, or non-invasive intervention indicated; moderate impact on ADL.
3. Severe: significant symptoms requiring invasive intervention; subject seeks medical attention, needs major assistance with ADL.

We will measure and compare rates of AEs across the four treatment arms. We will specifically look for common treatment-related AEs that include: LBP, soreness at the treatment site, gastrointestinal symptoms, emotional discomfort, and other events. We will capture AEs prospectively from study participants through monthly surveys and at in-person/videoconference/telephone visits. Each unique occurrence will receive a separate ID in order to avoid duplication in documentation.

[figure not shown]
SAE is generally defined as any untoward medical occurrence that results in death, is life threatening, requires inpatient hospitalization or prolongation of existing hospitalization, results in persistent or significant disability/incapacity, or is a congenital anomaly or birth defect.

We will collect SAEs both passively through ad hoc reporting and through systematic evaluation at study visits. Given the nature of the interventions we do not anticipate any specific treatment-related SAEs and therefore focus on standard and LBP-specific serious events: death; severe or permanent disabilities; life-threatening conditions; hospitalizations; other important medical events; progressive neurological deficits, or cauda equina syndrome.

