5.4 Adherence Assessment

The total number of treatments will be decided by the treating clinician based on each individual participant’s clinical presentation and response to care, as is done in clinical practice. We anticipate 4-6 visits being prescribed for most participants receiving SMT, 4-8 visits for most participants receiving SSM, and 2-4 visits for most participants receiving medical care. Participant adherence to assigned interventions will be documented at each visit in the clinical notes.

Treatment adherence has been defined in the Threshold Criteria for Transition as attending $\geq 75\%$ of prescribed intervention visits. We have expanded on this definition by including a minimum number of visits for each intervention and requiring participants not drop out of active care to be considered adherent. A minimum of 2 sessions will be required for participants in SMT and MC, and minimum of 4 for the two groups receiving SSM, but additional sessions may be needed.

Intervention fidelity will be assessed by review of treatment visit activities that address required, allowed and prohibited interventions. In addition, fidelity will be assessed by video/audio recordings or in person observations of randomly determined intervention visits. Fidelity assessments will occur monthly, for six months, on each provider currently treating patients, then quarterly thereafter. If concerns arise during quarterly reviews, the provider may resort back to monthly fidelity checks as needed. The DCC will monitor the treatment administered forms for activities defined as ‘out of scope’ for the defined intervention (e.g., spinal manipulation delivered to a participant assigned to structured self-management). Out of scope activities indicating potential crossover will be flagged through automated real-time alerts created by the DCC which will immediately be sent to the relevant site’s PI and study coordinators. The site study coordinators are best suited for contacting providers, as they will be familiar to them and will have developed collaborative working relationships that ensure successful project implementation. Additional actions would include remedial training for the providers and potential removal from providing study care.

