Subgroup/Moderator Analyses: We will consider two pre-specified subgroup analyses to look at treatment effects within: subjects who are medium risk based on STarT Back, and subjects who are high risk; and subjects stratified based on their duration of LBP. Subgroup analyses will use logistic or linear regression among restricted subsets to quantify specific treatment effects, and formal evaluation of differences in treatment effects across subgroups will be conducted using treatment by subgroup interactions. In addition to the pre-specified subgroup analyses we will also conduct exploratory analyses to evaluate the heterogeneity of treatment effects according to Gender, Race, and Ethnicity.

Responder Analysis: We will focus on evaluation of a >50% improvement in pain or function from baseline to six months, and from baseline to one year. We will also consider a >30% improvement, and a comprehensive responder analysis that looks at the cumulative percentage of subject achieving a range of improvement percentages as described in Farrar, Dworkin, and Max.⁷⁶

Secondary Outcomes: We will assess secondary outcomes including the PROMIS-29 measure, productivity loss, healthcare utilization (e.g., opioid use, injection, MRIs), and AEs for the combined group (SMT+SSM) and each intervention alone relative to MC. We will use linear or logistic regression and the Four Group model structure given above and will use linear mixed models or generalized estimating equations (GEE) for longitudinal analysis of secondary outcomes.¹⁵⁴

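### The between-arm AE comparison does not state its reporting source, although providers ask about AEs at every visit and MC has fewer anticipated visits than SMT or SSM

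*Combined protocol and SAP*

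**What the plan says.** Section 7.3 plans the comparison in one sentence: "We will measure and compare rates of AEs across the four treatment arms". The same paragraph names monthly surveys and visits (in person, by video or by telephone) as the routes of capture. Section 9, under Secondary Outcomes, makes the comparison inferential. It applies linear or logistic regression with the four-group model to several outcomes, "and AEs for the combined group (SMT+SSM) and each intervention alone relative to MC".

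On visits, section 7.1 says that "participants will be asked about the occurrence of AE/SAEs by their treatment provider at every visit", and section 6.2.4 repeats this. Sections 3.5 and 6.2.3 say that providers cannot be blinded. Section 5.4 gives the expected contact: "We anticipate 4-6 visits being prescribed for most participants receiving SMT, 4-8 visits for most participants receiving SSM, and 2-4 visits" for most participants in medical care. For adherence it adds: "A minimum of 2 sessions will be required for participants in SMT and MC, and minimum of 4 for the two groups receiving SSM". No anticipated range is given for SMT+SSM.

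On surveys, sections 6.1 and 6.2.4 schedule an AE question in months 1-12 for every arm. Sections 6.2.4 and 7.1 limit that question to events associated with the study interventions, whereas section 7.3 records AEs whatever their relationship. Section 7.5 assigns visits to the intervention phase and surveys to the follow-up phase, which does not match surveys from month 1.

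No section says which source feeds the comparison, over what period, or how unequal contact is handled.

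**The concern.** If both routes feed the comparison, as section 7.3 naturally reads, the number of times a participant is asked about AEs depends on the arm. With equal true event rates, the arm that is asked less often will tend to record fewer events, and that arm is MC. Section 2 sets the AEs of drug treatment against the low-risk profile of SMT, so a surplus of recorded AEs in SMT, SSM or SMT+SSM would matter. As planned, such a surplus could reflect real harm, more frequent questioning, or both, and the analysis gives no means of telling them apart.

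Two existing provisions do not deal with this. The separate ID for each occurrence (section 7.3) prevents double counting but does not equalise ascertainment. The statement in section 3.1 that differences in time and attention are not controlled concerns non-specific treatment effects, not AE detection.

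**Working it through.** The plan gives no power, alpha or expected rate for AEs, so there is no planned figure to reproduce. What can be checked is the imbalance in scheduled queries.

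**Inputs.** Visits (section 5.4), midpoints: MC (2+4)/2 = 3; SMT (4+6)/2 = 5; SSM (4+8)/2 = 6. Surveys (section 6.1): 2 in the 8-week phase and 12 over 12 months, in every arm.

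**Visits alone, relative to MC**
- SMT: 5/3 = 1.67 (low ends 4/2 = 2.0; high ends 6/4 = 1.5; extremes 4/4 = 1.0 to 6/2 = 3.0).
- SSM: 6/3 = 2.0 (low ends 4/2 = 2.0; high ends 8/4 = 2.0; extremes 4/4 = 1.0 to 8/2 = 4.0).
- SSM to SMT: 6/5 = 1.2.

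**Visits plus surveys**

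| Period | MC | SMT | SSM | SMT:MC | SSM:MC |
|---|---|---|---|---|---|
| 8 weeks | 3+2 = 5 | 5+2 = 7 | 6+2 = 8 | 1.40 | 1.60 |
| 12 months | 3+12 = 15 | 5+12 = 17 | 6+12 = 18 | 1.13 | 1.20 |
| Surveys only, 12 months | 12 | 12 | 12 | 1.00 | 1.00 |

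Using the low and high ends of the visit ranges, the 8-week ratios are 6/4 = 1.50 and 8/6 = 1.33 for SMT, and 6/4 = 1.50 and 10/6 = 1.67 for SSM. Visits for recurrence in months 3-12 are not counted, because the documents give no number for them.

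**From queries to recorded events.** This step needs assumptions that the documents do not supply. Three illustrations, all with equal true burden in every arm, show the range.

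1. *Each query independently yields a recorded AE with probability 0.05.* The proportion with any AE recorded is 1 - 0.95^n for n queries. Over 8 weeks this is 22.6% MC, 30.2% SMT and 33.7% SSM (ratios 1.33 and 1.49). Over 12 months it is 53.7%, 58.2% and 60.3% (ratios 1.08 and 1.12). Section 9 expects about 300 in MC, 300 in SSM and 200 in SMT, with 90% follow-up, giving 270, 270 and 180. At two-sided 0.05, the chance of a nominally significant difference from MC with no true difference is then 44% (SMT) and 82% (SSM) over 8 weeks, and 15% and 34% over 12 months.
2. *Each query captures a given event with probability p.* For SSM against MC over 8 weeks the ratio is [1 - (1-p)^8]/[1 - (1-p)^5]: 1.39, 1.24, 1.13, 1.07 and 1.01 for p = 0.1, 0.2, 0.3, 0.4 and 0.6. The formula treats every query as able to capture the event, including queries made before it, so these values are not bounds.
3. *An event is captured only if a query follows within w days.* Events are uniform over 56 days, visits evenly spaced and surveys at days 28 and 56 (20,000 simulated events per arm and window). The ratios to MC are 1.46 (SMT) and 1.96 (SSM) for w = 3, 1.52 and 1.80 for w = 7, and 1.00 and 1.00 for w = 14.

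The distortion therefore runs from none to nearly two-fold, depending on how long participants remember and report an event.

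**The case against.** **The source may already be the survey.** Section 3.2 lists AEs among patient-reported measures, and section 6.2.4 lists them as a secondary outcome under monthly follow-up. Pooling is therefore inferred, not stated. This stands as a limit on the claim. However, section 7.3 names both routes in the paragraph that announces the comparison, and nothing restricts it.

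**The common surveys dilute the imbalance.** They do, as the table shows. Three features keep them from removing it: only two fall in the treatment phase, their question is narrower, and section 7.2 says that SMT reactions usually resolve within a day, so a monthly question may miss them.

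**Contact in MC may be understated.** Section 5.1.4 allows telephone encounters in MC, and section 5.4 does not say whether its 2-4 visits include them. SMT and MC also share the minimum of 2 sessions, and the anticipated ranges meet at 4. This stands, and is why actual visits per arm should be reported.

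**More sessions can cause more events.** Soreness after a session is a real consequence of the assigned strategy, so an excess need not be an artefact. This also stands.

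**A survey-only comparison could err the other way.** It would rest on events that unblinded participants attribute to treatment. If an event first raised at a visit is de-duplicated out of the survey set, SMT and SSM would lose more events than MC. This rules out replacing the all-source comparison, but not adding to it.

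**The detail may sit elsewhere.** Sections 6.2.2 and 7.6 point to the Data Safety Monitoring Plan, which is only named in section 15. It may specify the source, and the sponsor can say so.

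**Conclusion.** The point holds as a risk that the plan leaves unhandled. The AE comparison does not specify its source, and visit-based questioning by unblinded providers is expected to be more frequent in SMT and SSM than in MC. The likely direction in an all-source comparison is relative under-recording in MC. The imbalance in scheduled queries is 1.40 (SMT) and 1.60 (SSM) over 8 weeks, and 1.13 and 1.20 over 12 months. These figures rest on midpoints of anticipated visits, two surveys in the treatment phase and no recurrence visits. For SMT+SSM only the minimum of 4 sessions is known.

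A reader might infer that the comparison is already biased about two-fold against the higher-contact arms. The documents do not support that. Two-fold describes SSM against MC on visits alone; SMT against MC is 1.67, SSM against SMT is 1.2, and the surveys shrink all three. Every figure for recorded events depends on an assumed capture or recall pattern, and some plausible patterns give no distortion. Nor can an excess in SMT or SSM be put down to questioning alone. The size of any bias cannot be derived from the documents.

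Comparative safety is not a listed objective and carries no alpha, so the primary analyses are unaffected. The change is still worth making before the AE tables are produced.

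**What to change.** In section 7.3 and under Secondary Outcomes in section 9, state that the between-arm AE comparison is presented by source:

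- Give a comparison based on the monthly survey responses (12 scheduled queries in every arm) beside the all-source comparison. Build it from the survey answers themselves, so that an event first raised at a visit is not lost from it.
- Keep visit-elicited events in the all-source comparison. Also tabulate visit-elicited and ad hoc events separately by arm, with the number of visits per arm.
- State that an all-source difference will not be attributed to treatment if the survey-based comparison does not show it, unless the events are transient ones that a monthly survey could miss.
- Reconcile the survey scope (intervention-associated events, sections 6.2.4 and 7.1) with the recording rule in section 7.3, and the phase split in section 7.5 with the survey schedule in section 6.1.

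The cost is a little more analysis; AE collection and reporting to the DSMB do not change. The survey comparison covers only events that participants attribute to the interventions and may miss short-lived ones, so it complements the all-source comparison and cannot replace it. The documents do not say outright that the reporting source is stored. Since AEs are scheduled separately at visits and in the monthly surveys, it should be recoverable, but the sponsor should confirm this.

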7.4 Reporting Procedures

Procedures and responsibilities for reporting AEs and SAEs are outlined in the figure below. “Awareness” in the figure below is defined as the date at which the research team is able to contact the participant to gather additional information about the event.

PACBACK: Reporting of AEs, UPs, and Protocol Noncompliance

November 30, 2017

If an AE occurs at a CCC where the PI is not available, the PI at the other CCC institution will be notified and the AE reporting protocol will be initiated. If both PIs are not available, a clinical Co-Investigator

will be notified, and the above protocol will be initiated. Once a PI is available, the PI will assume responsibility for reporting.

7.5 Follow-up for Adverse Events

AEs/SAEs will be identified during the intervention phase at study visits and during the study follow-up phase using monthly self-report questionnaires (surveys) or through direct contact with study staff. Events will be followed until resolution or stabilization, whichever occurs first; resolution and stabilization will be determined by the PI with input from the study clinician when appropriate.

If an AE/SAE occurs during the intervention phase, the study clinician will monitor the AE/SAE while the participant is under their care, this will include a medical evaluation and treatment, or modifications to treatment as necessary to protect the participant and minimize harm. If warranted, referral to an outside provider will be made.

If an AE/SAE occurs during the follow-up phase, study staff will be in regular contact with the participant as the event permits.

